Given that the intervention being tested requires parent adherence to recommendations (e.g., communicating with 211LA, keeping referral and service appointments) to achieve success, we will use an intention-to-treat analysis. Our analyses will be based on measuring differences between the intervention and comparison groups with respect to the above outcome variables. Additionally, covariate-adjusted differences will be evaluated using multivariable regression models. Incomplete variables will be handled using a multiple imputation approach with 10 imputations for multivariable analyses; imputations will be based on an iterative Markov chain Monte Carlo method, with initial values generated by an expectation–maximization algorithm. Finally, secondary analyses for all outcomes will include group*developmental screening risk category (low, moderate, high), or group*gender (female, male) interactions to explore differential intervention effects.

Hypothesis 1: A higher proportion of families in the intervention group will a) be successfully referred to early childhood service organizations for evaluation, and b) receive services, than families in the usual care group.

We will use multivariable logistic regression models for each of these binary outcome variables with group assignment as the main predictor, controlling for socio-demographic variables.

Secondary analyses will use the fact that multiple types of services may be indicated. This will allow us to examine specific services in isolation as binary outcome variables in logistic regressions. It is possible that certain types of services are more likely to be recommended or taken up than others. It is also possible that receipt of any vs. no services is too crude to distinguish among different types or severities of developmental needs. Thus, examining specific services may prove to be important adjunct analyses.

Hypothesis 2: Over time, formal developmental assessment scores in the intervention group will improve more than scores in the usual care group.

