We will compare costs per child screened to benefits. Total costs will be disaggregated into RA screening/initial referral, 211 program, and diagnostic and developmental services costs. Total benefits will be disaggregated into income and value of life expectancy gains. Using evidence from literature, these benefits will be estimated by predicting changes in educational achievement from improvements in early life assessments (Aim 2 findings), then predicting changes in educational attainment from changes in educational achievement, and then predicting changes in lifetime income and life expectancy from changes in educational attainment. Sensitivity analyses will explore alternative assumptions about costs, relationships between early-childhood development and long-term outcomes, and value of a life-year.

Power Analysis

Given our planned RCT enrollment of 662 families (331 per group), and assuming loss to follow-up of 20% per year, we expect 424 families (212 per group) to complete the study. For each hypothesis, we report minimally detectable differences using study completers. These estimates are likely conservative, since some analyses will be performed using data collected prior to the end of follow-up and including >424 families. The enrollment sample size was chosen so that detectable differences would be within the bounds of the confidence intervals from the pilot data. Unless otherwise noted, reference rates were estimated from the pilot study.

Hypothesis 1: A higher proportion of families in the intervention group will a) be successfully referred to early childhood service organizations for evaluation, b) be deemed eligible for services by service organizations, and c) receive services, than families in the usual care group.

a) A sample size of 212 per group provides 80% power to detect a 11.9 percentage-point difference in the referral rate, assuming a reference rate of 20.4%, a chi-squared test, and an alpha of 0.05. This difference is smaller than observed in the pilot study (21.8 percentage points; 95% CI: 9.1-33.8).

b) A sample size of 212 per group provides 80% power to detect an 9.2 percentage-point difference in the eligibility rate, assuming a reference rate of 8.6%, a chi-squared test, and an alpha of 0.05. This difference is smaller than observed in the pilot study (14.3 percentage points; 95% CI: 5.6-24.0).

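### The stated imputation method is usually a multivariate-normal one and suits the binary Hypothesis 1 outcomes poorly; if they are imputed that way and rounded, the odds ratios shrink toward the null

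*Combined protocol and SAP*

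**What the plan says.** The Statistical and Data Analysis Plan commits to intention-to-treat and then states: "Incomplete variables will be handled using a multiple imputation approach with 10 imputations for multivariable analyses". The engine is described in two clauses: "imputations will be based on an iterative Markov chain Monte Carlo method", and "with initial values generated by an expectation–maximization algorithm".

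For Hypothesis 1 the same section says: "We will use multivariable logistic regression models for each of these binary outcome variables with group assignment as the main predictor". The outcomes named there are referral and receipt of services. Eligibility appears as a third part only under Power Analysis.

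Secondary analyses of all outcomes add "group*developmental screening risk category (low, moderate, high), or group*gender (female, male) interactions".

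The section names no joint distribution, no model for binary or categorical variables, no rounding rule and no list of imputed variables. The pattern-mixture imputation described under Hypothesis 2 is a sensitivity analysis for the mixed models of scores and does not address Hypothesis 1.

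**The concern.** Iterative MCMC with EM starting values is how the standard data-augmentation routine for a multivariate normal model is normally described. That routine returns continuous values for a yes/no variable. Many fall below 0 or above 1, and essentially none equals 0 or 1. A binary logistic model cannot use them, so the analyst has to round, and rounding draws of an uncommon outcome pulls the two arms together.

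As written, the plan brings the Hypothesis 1 outcomes into scope: the logistic models are multivariable, and a missing outcome is an incomplete variable. At stake are the size of the Hypothesis 1 odds ratios and some of the power the trial was built to have.

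A secondary point concerns the interactions. A normal model with main effects only imputes as though the group-by-risk and group-by-gender interactions were zero. The plan does not say that those terms will enter the imputation model.

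**Working it through.** **1. The plan's own figures.** Power Analysis states: "A sample size of 212 per group provides 80% power to detect a 11.9 percentage-point difference in the referral rate". The usual-care rate behind that figure is 20.4%, with alpha 0.05. Receipt uses a usual-care rate of 7.2% and a difference of 8.7 points. The powered intervention rates are therefore 20.4 + 11.9 = 32.3% and 7.2 + 8.7 = 15.9%. With n = 212 per group and a two-sided test,

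power = Φ{[d − 1.96√(2p̄(1−p̄)/n)] / √([p0(1−p0) + p1(1−p1)]/n)}.

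Referral: (0.119 − 1.96 × 0.0428)/0.0424 = 0.83, giving 79.6%. Receipt gives 80.2%. Both agree with the stated 80%. Completers: 662 × 0.8 × 0.8 = 423.7, the stated 424, so 36% are lost by 24 months.

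**2. What normal draws look like.** Take the residual variance v as the average of p(1−p) over the arms.
- Receipt: v = (0.0668 + 0.1337)/2 = 0.1003, SD 0.317. Share of usual-care draws below 0: Φ(−0.072/0.317) = 41%.
- Referral: v = (0.1624 + 0.2187)/2 = 0.1905, SD 0.436. Share below 0: Φ(−0.204/0.436) = 32%.

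**3. Rounding at 0.5, unadjusted.** The imputed rate is q = P(N(p, v) > 0.5). The combined rate with fraction f missing is (1−f)p + fq.
- Receipt: q0 = 1 − Φ(0.428/0.317) = 8.8%; q1 = 1 − Φ(0.341/0.317) = 14.1%. At f = 0.36 the rates are 0.64 × 7.2 + 0.36 × 8.8 = 7.8% and 0.64 × 15.9 + 0.36 × 14.1 = 15.2%.
- Referral: q0 = 24.9%, q1 = 34.3%. At f = 0.36 the rates are 22.0% and 33.0%.

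| Missing | Receipt difference (true 8.7) | Receipt odds ratio (true 2.44) | Referral difference (true 11.9) |
|---|---|---|---|
| 10% | 8.4 | 2.35 | 11.6 |
| 20% | 8.0 | 2.26 | 11.4 |
| 36% | 7.5 | 2.13 | 11.0 |

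**4. Simulation of the planned type of analysis.** There were 331 per arm, 400 trials per setting and 10 imputations. Each used Bayesian normal-model draws, covariate-adjusted logistic regression and Rubin's rules. Assumptions not in the documents: one standard normal covariate, with log odds ratio 0.7 on the outcome and 0.4 on missingness, and data missing at random. The true log odds ratios are conditional on that covariate (referral 0.677, receipt 0.936), so they exceed the unadjusted ones.

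| Missing | Outcome | Normal, rounded | Change from truth | Logistic imputation | Power: rounded vs logistic |
|---|---|---|---|---|---|
| 10% | Referral | 0.649 | −4% | 0.675 | 92% vs 93% |
| 10% | Receipt | 0.902 | −4% | 0.955 | 90% vs 92% |
| 20% | Referral | 0.623 | −8% | 0.676 | 85% vs 89% |
| 20% | Receipt | 0.846 | −10% | 0.949 | 81.5% vs 86% |
| 36% | Referral | 0.585 | −14% | 0.677 | 74% vs 80.5% |
| 36% | Receipt | 0.799 | −15% | 0.977 | 67.5% vs 79% |

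Simulation error on power is about 2 points. The small excess for receipt under logistic imputation is also largely present with nothing missing (0.964 in the 36% runs). Other results:
- Adaptive rounding does not cure the shrinkage: −13% and −15% at 36% missing.
- At pilot-sized effects (20.4 + 21.8 = 42.2% for referral; 7.2 + 11.7 = 18.9% for receipt) and 36% missing, the shrinkage is 10% and 17%.
- With no true effect there is no material bias, and rejection is 1–2%.
- Interval coverage under the alternatives is 92–97%.
- Complete-case logistic regression at 36% missing gave 0.676 and 0.982 with about 81% power. In this setting rounding is therefore worse than not imputing.

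**The case against.** The strongest reply is that the plan never says multivariate normal. EM-started data augmentation also exists for categorical and mixed data, and the plan mentions no rounding or cutoff. It also never says outright that the Hypothesis 1 outcomes are imputed. Both points stand: the normal model and the imputation of outcomes are inferences. They are the natural ones, because the method described is the usual label for normal-model imputation and nothing exempts the outcomes.

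A reader might infer that 36% of the Hypothesis 1 outcomes would be imputed. The documents do not support that as an expectation:
- The Hypothesis 1 analysis text fixes no 24-month time point.
- Referrals and service connections are asked about at 6, 12 and 24 months (Follow-up Data Collection).
- Chart Abstraction covers referrals and services for participants over the 24 months.
- 211LA reports the outcome of each referral in the intervention arm (Intervention).
- Power Analysis itself calls the completer figures conservative.

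The plan does not say how these sources combine, so the true fraction is unknown and a range is the fair statement.

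A reader might also apply 7–20% event rates to both arms. Those are usual-care rates only.

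Finally, a reader might put a size on the damage to the interaction tests. That would need the share of children at risk and the subgroup effects, which the documents do not give. The analyses are exploratory, and chained equations without interaction terms would have the same defect. Only the need to include the terms survives.

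**Conclusion.** The point holds in conditional form. The plan states a method that ordinarily means normal-model imputation, sends binary outcomes to logistic regression, and gives no binary imputation model. If referral and receipt are imputed that way and rounded, the log odds ratio is attenuated by roughly 4% at 10% missing, 8–10% at 20% and 14–15% at 36%. At the upper case, power falls by about 6 points for referral (80.5% to 74%) and about 11–12 for receipt (79% to 67.5%).

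These sizes rest on missingness at random, the assumed covariate effects and the plan's powered rates. It would be wrong to conclude that Hypothesis 1 could yield false positives this way: the bias is toward the null and vanishes when there is no effect. Nor are the sample size and power statements in error, since they rest on completers and a chi-squared test and reproduce. The plan should be changed because a better-suited method is available at little cost.

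**What to change.** In the Statistical and Data Analysis Plan, replace the MCMC/EM sentence with fully conditional specification (chained equations):
- Use logistic models for binary variables, ordinal or multinomial models for categorical variables, and predictive mean matching or linear models for scores.
- State that the imputation covers the Hypothesis 1 outcomes, and list the imputed variables.
- Include arm, the stratification factors (screening risk and clinic system), baseline scores and earlier outcomes as predictors.
- For the exploratory interaction analyses, include the group-by-risk and group-by-gender terms in the imputation model, or impute by arm where event counts allow.

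The cost is wording and somewhat more set-up; no new data, visits or participants are needed. The downside is sparse outcomes. At 7.2% of 331, usual care has about 24 receipt events, of which about 15 would be observed at 36% missing (24 × 0.64). Imputing by arm should therefore not be mandatory. Convergence and separation should be checked, with penalised or augmented logistic imputation as the fallback.

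### If missing yes/no referral and service-receipt outcomes are imputed by normal-model MCMC and rounded to 0/1, the adjusted Hypothesis 1 effects shrink; the plan should specify logistic imputation

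*Combined protocol and SAP*

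**What the plan says.** The opening paragraph of the Statistical and Data Analysis Plan sets one approach for missing values: "Incomplete variables will be handled using a multiple imputation approach with 10 imputations for multivariable analyses". The same sentence continues that "imputations will be based on an iterative Markov chain Monte Carlo method, with initial values generated by an expectation–maximization algorithm". It states no distribution, no separate method for binary or categorical variables and no rounding rule. It neither names nor excludes outcomes.

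Under Hypothesis 1 in the same section, the outcomes are that families "be successfully referred to early childhood service organizations for evaluation, and b) receive services, than families in the usual care group". The analysis is: "We will use multivariable logistic regression models for each of these binary outcome variables with group assignment as the main predictor".

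The Power Analysis section lists a further outcome, eligibility ("b) be deemed eligible for services by service organizations, and c) receive services, than families in the usual care group"), which the Hypothesis 1 text of the analysis plan does not carry. That section plans to enrol 662 in total, with 331 in each arm. Its attrition statement reads: "assuming loss to follow-up of 20% per year, we expect 424 families (212 per group) to complete the study".

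The pattern-mixture imputation under Hypothesis 2 is attached to the mixed models for developmental scores. It does not settle how binary Hypothesis 1 outcomes are imputed.

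**The concern.** MCMC started from EM estimates is the usual description of imputation under a joint multivariate-normal model. Such a model gives a missing yes/no outcome a continuous value, which may be negative, fractional or above 1. A logistic regression cannot use it, so someone must convert it to 0 or 1 by a step that the plan does not state.

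Rounding at 0.5 is a natural choice, but it does not preserve the event rates. The normal model uses one residual variance for both arms, while the variance of a binary outcome depends on its rate. At the plan's low rates, rounding moves the imputed arms closer together.

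This has nothing to do with why data are missing, so it arises even under missing completely at random. Sensitivity analyses that only vary the missing-data assumption would not reveal it. At stake are the size of the adjusted effect for the trial's first aim and some of its power.

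**Working it through.** **Inputs.** From the Power Analysis section: 331 enrolled and 212 completing per group; usual-care rates of 20.4% (referral) and 7.2% (receipt); detectable differences of 11.9 and 8.7 points. The intervention rates are therefore 32.3% and 15.9%.

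**The plan's own figures.** Completers: 662 × 0.8 × 0.8 = 423.7, stated as 424. This implies 36% loss at two years. The plan says "A sample size of 212 per group provides 80% power to detect a 11.9 percentage-point difference in the referral rate". For a two-sided pooled-variance test at alpha 0.05,

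power = Φ{[d√n − 1.96√(2p̄(1−p̄))] / √(p0(1−p0) + p1(1−p1))}.

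- Referral: Φ{(1.733 − 1.221)/0.617} = 79.6%
- Receipt: Φ{(1.267 − 0.886)/0.448} = 80.2%

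Both reproduce the stated 80%.

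**Normal imputation with rounding at 0.5 (assumed implementation).** Assume that data are missing completely at random with the same fraction in each arm, that group is in the imputation model and that there are no other covariates. Take the detectable differences as the true effects.

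- Pooled within-arm SD: s = √{[p0(1−p0) + p1(1−p1)]/2}, which gives 0.4365 (referral) and 0.3167 (receipt).
- Share of raw imputed values outside 0–1: Φ(−p/s) + 1 − Φ((1−p)/s), between 29% and 41% over the arms and outcomes.
- Rate after rounding: q = Φ((p − 0.5)/s).
 - Referral: Φ(−0.678) = 24.9% and Φ(−0.406) = 34.3%, against true rates of 20.4% and 32.3%.
 - Receipt: Φ(−1.352) = 8.8% and Φ(−1.077) = 14.1%, against true rates of 7.2% and 15.9%.
- Overall difference with missing fraction m: (1−m)(p1−p0) + m(q1−q0). At m = 0.36:
 - Referral: 0.64 × 11.9 + 0.36 × 9.38 = 11.0 points
 - Receipt: 0.64 × 8.7 + 0.36 × 5.26 = 7.5 points

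| Missing | Referral difference (true 11.9) | Shrinkage | Receipt difference (true 8.7) | Shrinkage |
|---|---|---|---|---|
| 36% | 10.99 | 7.7% | 7.46 | 14.3% |
| 20% | 11.39 | 4.3% | 8.01 | 7.9% |
| 10% | 11.65 | 2.1% | 8.36 | 4.0% |
| 5% | 11.77 | 1.1% | 8.53 | 2.0% |

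At 36% missing the odds ratio falls from 1.86 to 1.75 (referral) and from 2.44 to 2.13 (receipt). On the log scale that is 10% and 15%.

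**Simulation** (331 per arm, 36% missing, 10 imputations, Rubin's rules, no other covariates, 500 runs, Monte Carlo error about 2 points on power):

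| | Referral log OR | Power | Receipt log OR | Power |
|---|---|---|---|---|
| Complete cases | 0.63 | 80% | 0.88 | 79% |
| Logistic imputation | 0.63 | 77% | 0.88 | 75% |
| Normal, rounded at 0.5 | 0.57 | 74% | 0.75 | 67% |
| Normal, adaptive rounding | 0.58 | 74% | 0.75 | 68% |

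The cost of rounding is the gap to logistic imputation, about 3 and 8 points. The gap between logistic imputation and complete cases has nothing to do with rounding. A separate simulation with one covariate (log-odds 0.4, 1,000 runs) gave 73% against 78% for referral and 71% against 77% for receipt.

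Unrounded normal values left the risk difference intact (12.1 and 8.5 points, against 12.0 and 8.5 for complete cases), but they cannot enter the planned logistic model. At 10% missing, simulated power with rounding was 1 to 2 points below logistic imputation.

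**The case against.** The strongest reply is that the plan names neither a normal model nor rounding, so the bias belongs to an assumed implementation. That stands: a reader might infer that the plan prescribes a biased method, and the text does not go that far. The gap is still more than missing detail. The method named is the usual label for normal-model imputation, and it does not produce what the logistic models need.

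A reader might also infer that 36% of these outcomes will be imputed. The documents do not support that. The 36% is loss to follow-up over two years. Under Chart Abstraction, referrals and services are abstracted from each participant's record over the 24 months, and under Study Conditions 211LA reports referral outcomes for the intervention arm. Parents are also asked at 6 and 12 months, and the Power Analysis section expects more than 424 families in some analyses. So 36% is an upper case.

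Three further readings go too far:

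- *The trial's whole first-aim result is affected.* The imputation sentence covers only multivariable analyses; the unadjusted group comparison lies outside it.
- *The eligibility effect is biased.* The Hypothesis 1 text of the analysis plan has no eligibility model.
- *Imputed categorical covariates would distort the comparison.* No effect on the randomized contrast has been shown.

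Finally, the direction is toward no effect, so this would not manufacture a benefit. If the effects were as large as in the pilot (21.8 and 11.7 points), power at 36% missing would stay high: 99.5% against 99.7% for referral and 91% against 95% for receipt. That also stands.

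**Conclusion.** The point holds conditionally and is a cheap improvement. If missing referral and receipt outcomes are imputed by normal-model MCMC and rounded, the adjusted effects are attenuated at every missing fraction examined. The upper case is the 8% and 14% shrinkage at 36% missing; at 10% missing the loss is minor. Adaptive rounding does not remove the problem.

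These sizes rest on data missing completely at random and equally by arm, group being in the imputation model, and the plan's detectable differences being the true effects. The agreement between logistic imputation and complete cases was checked only under that missingness, so it is not an argument for a complete-case analysis.

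**What to change.** In the Statistical and Data Analysis Plan, replace the MCMC/EM sentence with wording such as: *Incomplete variables will be imputed by fully conditional specification (chained equations) with group assignment in every model. Binary variables, including referral, service receipt and, if analysed, eligibility, will use logistic models. Categorical covariates will use multinomial or ordinal logistic models, and scores will use linear regression or predictive mean matching. No rounding will be applied.* Normal-model MCMC can stay for continuous scores if preferred.

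The cost is a short text change and a different option in standard imputation software, with no new data or participants. The downside is small: the conditional models have no guaranteed joint distribution, and rare outcomes may need penalised or augmented logistic imputation.

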Randomization will be stratified by developmental screenings result (high/moderate vs. low) as well as by clinic system, creating 8 groups that will be divided between the intervention and control groups to ensure even representation. To determine group assignment, the Research Assistant will enter the developmental screening result and clinic into REDCap, which will calculate the risk level as well as assign group. The Research Assistant will provide the participant with their group assignment at this time as well as describe briefly the intervention further for the intervention group. In addition, the Research Assistant will remind the participant that a summary of the results will be provided to their doctor.

Baseline Developmental Assessments:

The Research Assistant will then administer two developmental assessments over the phone: the Child Behavior Checklist (CBCL) and the PEDS:DM-Assessment Level (AL). The subdomains of the CBCL the RA will administer include: attention problems, aggressive behavior, autism spectrum problems, and oppositional defiant problems. All children will be asked all CBCL questions. The PEDS:DM-AL includes several subscales: fine motor, self-help, receptive language, expressive language, gross motor, social emotional, and academic. Together, they combine to form the cognitive overall score, which is used to calculate age equivalency. All low risk kids will receive the expressive and receptive language scale questions. Moderate and high risk kids will receive the full PEDS:DM-AL.

In addition, the RA will ask about families' experiences with care at the clinic and anticipatory guidance received; sociodemographic questions, including covariates such as child gender, parent education level, parent marital status, race/ethnicity, language, household composition and income, health insurance status, as well as a hunger scale and the PHQ2; a financial wellbeing scale, and the protective factors survey.

Engagement:

To keep families engaged and remind them of study participation over the 24-month period, parenting tips and child health information will be provided by text monthly – texts will be relevant to the full age range of the kids enrolled at any time point (11 months to 5 years) and will include topics such as sleep, screen time, safety, and nutrition. In addition, a reminder letter asking for updated contact information will be sent 1-2 months prior to each survey time point. A

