The 6-month survey includes the M-CHAT-R for children who were too young at baseline to receive the screening. No other developmental screenings will be administered at 6, 12, or 24 months. The Child Behavior Check List will be administered at 6, 12, and 24 months and the PEDS:DM-AL will be administered in the same fashion as baseline at 12 and 24 months, as will experiences with care and anticipatory guidance. At all follow-up time points, participants will be asked about referrals and connections to services and those in the intervention group will be asked about their experiences with 211 at 6 months. At each follow-up time point, the RA will call and text a study participant up to 20 times each (10 calls, 10 texts) to connect for the interview, unless otherwise specified by the family. We will contact by email study participants that we have already contacted by phone but haven't been able to reach to complete the follow-up surveys.

Chart Abstraction:

Medical record review will occur at baseline and throughout the study time period. The RA will conduct electronic health record reviews for each of the study participants. They will assess developmental surveillance, developmental screening (validated screening tool use), and documentation of referrals and services from birth to baseline as well as in the 24 months of the study period. After completing site-specific training and documentation, the RA will be provided with an administrative login for each site's electronic health / medical record. They will use this to log in to access the electronic medical record and review the study participant's record for the noted elements. In addition, the RA will review for process measures – including the attendance of the scheduled baseline well child check-up, upload of developmental screening results into the medical record, as well as upload of the care plan and care coordination outcome summary.

Statistical and Data Analysis Plan:

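### Randomisation is stratified by screening risk and clinic system, but no main Hypothesis 1 or 2 model names either factor; if the strata are prognostic this gives up some power (under assumed stratum effects, about 1 to 6 points for referral and less elsewhere)

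*Combined protocol and SAP*

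**What the plan says.** The Randomization section states: "Randomization will be stratified by developmental screenings result (high/moderate vs. low) as well as by clinic system". With two risk levels and four clinic systems there are eight strata, and their purpose is given as "creating 8 groups that will be divided between the intervention and control groups to ensure even representation". Balance is thus the aim, but no allocation method (such as permuted blocks) is given.

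The Statistical and Data Analysis Plan specifies the Hypothesis 1 logistic models "with group assignment as the main predictor, controlling for socio-demographic variables". The nearest thing to a list of those variables is under Baseline Developmental Assessments: "covariates such as child gender, parent education level, parent marital status, race/ethnicity, language, household composition and income, health insurance status". It is open-ended and contains neither stratification factor. In this section Hypothesis 1 covers only two outcomes, that families will "be successfully referred to early childhood service organizations for evaluation, and b) receive services, than families in the usual care group". Eligibility appears only in the Power Analysis version of the hypothesis.

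The main Hypothesis 2 analyses are linear regressions of change from baseline by arm, with no covariates named. Socio-demographic adjustment is mentioned only for the exploratory mixed models.

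Risk category enters only here: "secondary analyses for all outcomes will include group*developmental screening risk category (low, moderate, high". Clinic system enters no model; the closest is a sensitivity analysis that clusters children by provider. The imputation text, "Incomplete variables will be handled using a multiple imputation approach with 10 imputations for multivariable analyses", does not say which variables the imputation model contains.

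**The concern.** When randomisation is stratified on prognostic factors, the analysis should normally condition on them. Conditioning recovers power whether or not the arms are balanced within strata. If they are balanced, an analysis that ignores the strata also overstates the variance of the treatment comparison, so its type I error falls slightly below 5%. With simple allocation, type I error stays at about 5% and only the power is forgone.

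A link between strata and outcome is plausible here. The risk stratum is the developmental screen result, which goes to the child's doctor in both arms, and the Hypothesis 1 outcomes are referral for developmental evaluation and receipt of services.

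The silence also leaves a choice open. Because the covariate list is open-ended, adjustment for risk or clinic could be decided after results are seen.

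**Working it through.** **1. The plan's own figures.** Inputs from the Power Analysis: 662 enrolled, 20% lost per year, so 662 × 0.8 × 0.8 = 423.7, stated as 424 (212 per group). With the pooled two-proportion formula, two-sided 5%:

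power = Φ{[d − 1.96·√(2·p̄(1−p̄)/212)] / √([p₀(1−p₀)+p₁(1−p₁)]/212)}

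- Referral, 20.4% vs 32.3%: Φ[(0.119 − 0.0839)/0.0424] = 79.6%
- Eligibility, 8.6% vs 17.8%: Φ[(0.092 − 0.0644)/0.0326] = 80.1%
- Service receipt, 7.2% vs 15.9%: Φ[(0.087 − 0.0608)/0.0308] = 80.2%

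The stated 80% therefore reproduces with no stratum adjustment. At the pilot differences (21.8, 14.3 and 11.7 points) the same formula gives 99.8%, 98.3% and 95.0%.

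**2. Binary outcomes: crude test against Mantel-Haenszel.** Simulation, 40,000 trials per scenario: 662 children over 8 strata, each retained with probability 0.64, the stated differences applied as a common odds ratio. Assumed, because the documents do not give them: 30%, 40% or 50% screen positive; risk odds ratio 3, 5 or 7; clinic SD 0 or 0.4 on the log-odds scale.

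| Outcome | Power gain, balanced | Crude type I error, balanced | Power gain, simple allocation | Power gain, all 662 observed (balanced) |
|---|---|---|---|---|
| Referral | 1.3–5.6 | 3.7–4.7% | 1.3–6.5 | 0.6–1.7 |
| Eligibility | 0.7–3.5 | 4.3–5.0% | 0.5–4.0 | 0.3–1.1 |
| Service receipt | 0.4–3.1 | 4.4–5.0% | 0.1–3.2 | 0.3–1.0 |

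Gains are in percentage points. Under simple allocation, crude type I error is 4.7–5.2%. If the strata are not prognostic, stratifying changes power by −0.5 to −0.2 points (balanced) or −0.9 to −0.6 (simple). The last column starts from crude power of 94–96%. The eligibility row applies only if that outcome is modelled like the other two.

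**3. Binary outcomes: the planned model form.** Logistic Wald test, 12,000 trials per scenario, 14 assumed non-prognostic binary covariates, balanced allocation, 40% positive, clinic SD 0.4.

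| Outcome | Gain at odds ratio 3, 5, 7 | Type I error without strata | Type I error with strata |
|---|---|---|---|
| Referral | 3.0, 5.0, 5.6 | 4.4–4.7% | 5.3–5.7% |
| Eligibility | 1.7, 2.6, 3.8 | 4.9–5.0% | 5.5–5.9% |
| Service receipt | 1.5, 2.4, 3.2 | 4.6–5.1% | 5.5–5.6% |

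With no stratum effect the gain is 0.2–0.3 points. Part of the gain in this table reflects the higher type I error. With only three covariates (4,000 trials), type I error with strata is 4.8–5.3% for referral and 4.5–5.0% for service receipt, so the inflation comes from the long covariate list. Without strata, conservatism in this long model is clear only for referral.

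**4. Hypothesis 2, all-children language score.** Stated effect size 0.27 with 212 per group, so nc = 0.27 × √106 = 2.780. Let R² be the assumed share of change-score variance explained by the strata.

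- Unadjusted, balanced: Φ[(nc − 1.96)/√(1−R²)]
- Unadjusted, after 36% random loss: Φ[(nc − 1.96)/√(1−0.64R²)]
- Unadjusted, simple allocation: Φ(nc − 1.96) = 79.4%
- Adjusted: Φ[nc/√(1−R²) − 1.96]

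| R² | Unadjusted, balanced | Unadjusted, after loss | Adjusted | Gain (after loss) |
|---|---|---|---|---|
| 2% | 79.6% | 79.5% | 80.2% | 0.6 (0.6) |
| 5% | 80.0% | 79.8% | 81.4% | 1.4 (1.6) |
| 10% | 80.6% | 80.2% | 83.4% | 2.8 (3.2) |

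At R² = 20% the balanced gain would be 5.4 points (82.0% to 87.5%, before rounding).

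**The case against.** The strongest reply is that no error has been shown. Power was calculated for an unadjusted chi-squared test and a t-test, so no promised power is lost, and there is no bias or type I inflation. At pilot-sized effects power is already at least 95%. That stands, and it limits the point to efficiency.

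Second, the size rests on assumed prognostic strength. That stands too. Socio-demographic terms correlated with clinic or risk may already absorb part of the effect.

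Third, the crude-versus-stratified comparison is not the planned logistic model, and in a 14-covariate model some of the gain is bought with type I error. In a further run of that setting (16,000 trials), holding the model with strata to a true 5% test cut the gains at odds ratios 3 and 5 to about 1.4 and 3.8 points (referral), 0.6 and 1.9 (eligibility), and 1.1 and 1.4 (service receipt). The gain is smaller but survives.

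Fourth, chart review covers "documentation of referrals and services from birth to baseline as well as in the 24 months of the study period", and the Power Analysis expects some analyses to include more than 424 families. If outcomes are available for all 662, the gain is under 2 points.

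Finally, the group-by-risk models would ordinarily carry the risk main effect, provider clustering partly reflects site, and restriction to screen-positive children fixes the two-level risk factor. These are secondary, sensitivity or subset analyses. They do not settle what the main models contain.

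**Conclusion.** The concern holds. No main Hypothesis 1 or 2 model names either stratification factor, and the open-ended covariate wording does not settle whether they belong. The consequence is forgone power and, if allocation is balanced within strata, a slightly conservative crude test. The results are not invalid.

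Under the assumed stratum effects and 36% random loss, the forgone power is about 1 to 6 points for referral and less for eligibility and service receipt. For the Hypothesis 2 language score it is about 1 to 3 points if the strata explain 2–10% of change-score variance; only well above that would it rival referral. It falls below 2 points for every Hypothesis 1 outcome if all 662 families contribute outcomes, and it is nil or slightly negative if the strata are not prognostic. The change is still worth making because the possible gain exceeds the possible loss of under one point. Confidence in the size is medium, since the documents give no outcome rates by risk or clinic.

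**What to change.** Name screening risk and clinic system as fixed effects in the Hypothesis 1 models and the all-children Hypothesis 2 models, and include both in the multiple imputation model. In the screen-positive Hypothesis 2 subset, use clinic system plus moderate vs high risk, because the two-level stratifier is constant there. For service receipt, keep risk at two levels. Optionally, add a Mantel-Haenszel comparison for the crude difference and report a standardised risk difference.

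The cost is SAP wording; both factors are already entered in REDCap at randomisation. The models spend four degrees of freedom with two-level risk (1 + 3) or five with three-level risk (2 + 3). This matters most for service receipt, with about 49 events among completers at the target effect (212 × 0.072 ≈ 15, plus 212 × 0.159 ≈ 34). With 14 other covariates, adding the strata moves its type I error from 4.6–5.1% to 5.5–5.6%, and 1.5–1.7% of null fits fail to converge (under 0.1% at the target effect). With three covariates type I error with strata is 4.5–5.0%, so a short, prespecified socio-demographic list should accompany the change.
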